## 7. RESEARCH QUESTION AND OBJECTIVES

The study will address the following primary research question: What is the frequency of readmission for major bleeding (MB) within 1 month after an index hospitalization for NVAF patients treated with apixaban, dabigatran, rivaroxaban, or warfarin?

- The primary objective of the study is to evaluate and compare 1-month MB-related readmission rates of hospitalized NVAF patients treated with dabigatran, rivaroxaban, or warfarin vs. apixaban.
- The secondary objectives are:
  - To evaluate and compare 1-month all-cause readmission rates of hospitalized NVAF patients treated with dabigatran, rivaroxaban, or warfarin vs. apixaban
  - To determine average hospital length of stay (LOS) and costs associated with MB-related and all-cause readmissions occurring within 1 month of initial hospitalizations of hospitalized NVAF patients treated with dabigatran, rivaroxaban, or warfarin vs. apixaban

Exploratory objectives:

- To describe 1-month stroke-related readmission rates of hospitalized NVAF patients treated with dabigatran, rivaroxaban, or warfarin vs. apixaban
- To describe average hospital LOS and costs associated with stroke-related readmissions occurring within 1 month of initial hospitalizations of hospitalized NVAF of patients treated with dabigatran, rivaroxaban, or warfarin vs. apixaban
- To describe readmission rates, hospital LOS and costs associated with all-cause, MB-related and stroke-related readmissions occurring within 3 months of initial hospitalizations of hospitalized NVAF of patients treated with dabigatran, rivaroxaban, or warfarin vs. apixaban

[figure not shown]
## **8. RESEARCH METHODS**

### **8.1. Study design**

The study will be a retrospective cohort analysis using the Premier Hospital database. The overall study period will be from January 1, 2012 through September 30, 2017, to allow for a 1 month follow up period for observation of readmissions and a 1-year baseline observation period. Adult patients (age  $\geq 18$  years) hospitalized for NVAF, based on a primary or secondary discharge diagnosis code indicating NVAF, will be identified from the Premier Hospital database between January 1, 2013 and June 30, 2017. Patients who received apixaban, dabigatran, rivaroxaban, or warfarin during any time of the hospitalization (from admission to discharge) will be identified and grouped into study cohorts based on the OAC initiated. The first of such NVAF hospitalizations will be defined as the index hospitalization. Patients with more than one type of OAC drug usage during the index hospitalizations will be excluded so that patients can be exclusively assigned into each OAC patient cohorts. Demographic, patient clinical characteristics, hospital characteristics, and key anticoagulant treatment-related information will be measured during the index hospitalization of NVAF patients. Other clinical characteristics (e.g. prior bleeding) of NVAF patients will be measured during a 12-month baseline period. The proportions of patients treated with apixaban, dabigatran, rivaroxaban, and warfarin that have MB-related, all-cause, and stroke-related readmissions that occur within 1 month of discharge of their initial hospitalization for NVAF will be evaluated. Hospital LOS and associated costs of MB-related, all-cause, and stroke-related readmissions will be determined and compared between the other OAC cohorts and the apixaban cohort.

Note: We anticipate that the sample size of patients treated with edoxaban is low and thus we have not included patients treated with edoxaban in this study evaluation. This is consistent with previous alliance NVAF studies.

**Figure 1. Study Time Periods** (for illustration purposes, may not be proportional)

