### 3. ABSTRACT

**Title:** Hospital Readmissions Among Nonvalvular Atrial Fibrillation Patients Treated with Oral Anticoagulants in the U.S.

**Version:** 1

**Date of Protocol:** March 26, 2018

**Author:** [name], MBA, Novosys Health; [name], JD, MPH, Pfizer

**Rationale and background:** Hospital readmission rates are a critical concern in the U.S. and in October of 2012 the Hospital Readmissions Reduction Program was implemented by the Centers for Medicare and Medicaid Services (CMS) to reduce the frequency of readmission among Medicare patients. It has therefore become increasingly important to examine hospital readmission rates and the factors associated with readmission. Although, readmission rates of NVAF patients have been studied to some extent in regard to all-cause readmissions, little information exists in the published literature on bleeding-related readmissions. We previously conducted an early evaluation that investigated rates of all-cause and bleeding-related readmissions among NVAF patients treated with dabigatran, rivaroxaban, and apixaban (January 1, 2012 through March 31, 2014). This current analysis will be a follow-up of our earlier assessment and will include in addition to NVAF patients treated with DOACs, patients treated with warfarin. Patients hospitalized for NVAF and treated with OACs will be identified from January 1, 2013 through June 30, 2017.

**Research question:** What is the frequency of readmission for major bleeding (MB) within 1 month after an index hospitalization for nonvalvular atrial fibrillation (NVAF) for patients treated with apixaban, dabigatran, rivaroxaban, or warfarin?

Note: we anticipate that the sample size of patients treated with edoxaban is low and thus do not include edoxaban in this study evaluation. This is consistent with previous alliance NVAF studies.

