### 8.2.1. Inclusion criteria

Patients must meet all the following inclusion criteria to be eligible for inclusion in the study:

- Have a hospital discharge ICD-9-CM code of 427.31 or 427.32 (and corresponding ICD-10 codes) indicating a primary or secondary diagnosis of AF identified from the Premier Hospital database between January 1, 2013 and September 30, 2017.
- Received any of the OACs, apixaban, dabigatran, rivaroxaban, or warfarin during any time of the hospitalization from admission to discharge
- Have an age  $\geq 18$  years as of the initial hospitalization with an AF diagnosis

Note: All the medical codings, e.g. ICD-9, ICD-10, CPT/HCPCS codes used in the patient selection criteria are consistent with the Eliquis Harmonized Retrospective Study Protocol.

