Index Stroke/Transient Ischemic Attack (TIA)	Patient characteristic and potential confounder	Patients with a stroke/TIA diagnosis on hospital records during their index hospitalization and reported as count and percentage.
Baseline Prior Stroke/TIA	Patient characteristic and potential confounder	Patients with a stroke/TIA diagnosis on hospital records during the baseline period and reported as count and percentage.
Index Hospitalization Congestive Heart Failure	Patient characteristic and potential confounder	Patients with a diagnosis on hospital records for congestive heart failure in the index hospitalization and reported as count and percentage.
Index Hospitalization Diabetes	Patient characteristic and potential confounder	Patients with a diagnosis on hospital records for diabetes in the index hospitalization and reported as count and percentage.
Index Hospitalization Hypertension	Patient characteristic and potential confounder	Patients with a diagnosis on hospital records for hypertension in the index hospitalization and reported as count and percentage.
Index Hospitalization Peripheral Vascular Disease	Patient characteristic and potential confounder	Patients with a diagnosis on hospital records for peripheral vascular disease in the index hospitalization and reported as count and percentage.

Variable	Role	Operational definition
Index Hospitalization Pulmonary Disease	Patient characteristic and potential confounder	Patients with a diagnosis on hospital records for pulmonary disease in the index hospitalization and reported as count and percentage.
Index Hospitalization DOAC Dose Strength	Patient characteristic and potential confounder	Patients with apixaban, dabigatran, and rivaroxaban dose strengths of high, low, and unknown during the index hospitalization and reported as count and percentage.
Other Anticoagulants During Index Hospitalization	Patient characteristic and potential confounder	Patients who receive enoxaparin, dalteparin, tinzaparin heparin, and fondaparinux during the index hospitalization and reported as count and percentage.
Index Hospital Geographic Region	Patient characteristic and potential confounder	East North Central, East South Central, Middle Atlantic, Mountain, New England, Pacific, South Atlantic, West North Central, West South Central. Reported as count and percentage

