### 8.7. Data analysis

Means  $\pm$  standard deviations, and medians will be provided for continuous variables. Numbers and percentages will be provided for dichotomous and polychotomous variables. Bivariate comparisons of baseline patient and hospital characteristics and readmission measurements will be provided, with appropriate tests (e.g., ANOVA test, chi-square test) used based on the distribution of the measure. A propensity score matching (PSM) 1:1 technique will be used to control for confounders when comparing each of the OAC cohorts vs. the apixaban cohort. A logistic regression analysis will be carried out on the matched patient cohorts to further evaluate the potential impact of treatment with the different OACs vs. treatment with apixaban on 1-month MB-related and all-cause readmissions. Only the index drug will be the covariate, since other patient characteristics are expected to be similar already after the PSM. Since the patient sample size attribution in the PSM process is not known, if the population sizes are not sufficient after the PSM attrition, a multivariable logistic regression analysis will be carried out to assess the potential impact of treatment with the different OACs compared to treatment with apixaban on 1-month MB-related and all-

cause readmissions, separately. The independent covariates in the regression analyses will include key patient demographics and hospital characteristics. The final list of such covariates will be determined with inputs from the Pfizer team. Additionally, we will carry out a two-part model analysis and a generalized linear model with log transformation and gamma distribution to examine the impact of treatment with the 3 different OACs vs. apixaban on MB-related and all-cause hospital readmission costs. Measurements related to exploratory objectives will be analyzed using descriptive statistics. All data analysis will be executed using statistical software SAS version 9.4.

Detailed methodology for summary and statistical analyses of data collected in this study will be documented in a Statistical Analysis Plan (SAP), which will be dated, filed and maintained by the sponsor. The SAP may modify the plans outlined in the protocol; any major modifications of primary endpoint definitions or their analyses would be reflected in a protocol amendment.

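### Index stays with AF as primary and as secondary diagnosis are pooled, while Table 1's confounder list names neither AF diagnosis position nor principal diagnosis, so the reason for admission is only partly controlled.

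*Protocol*

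**What the plan says.** **Population.** Section 8.1 (repeated in the abstract and section 8.2) takes adults "hospitalized for NVAF, based on a primary or secondary discharge diagnosis code indicating NVAF". Section 8.2.1 likewise asks for a discharge code "indicating a primary or secondary diagnosis of AF identified from the Premier Hospital database". The abstract's research question is about readmission "within 1 month after an index hospitalization for nonvalvular atrial fibrillation (NVAF) for patients treated with" one of the four anticoagulants. The objectives in section 7 refer instead to hospitalized NVAF patients, and the section 7 form of the question can be read as any hospitalization of a patient who has NVAF.

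**Confounders.** Table 1 marks each variable as a potential confounder. It covers demographics, payer, Charlson index, stroke and bleeding scores, prior bleed, prior and index stroke/TIA, several index-stay comorbidities, DOAC dose strength, other anticoagulants and hospital traits. The comorbidities are recorded as present or absent, for example "Patients with a diagnosis on hospital records for congestive heart failure in the index hospitalization", without regard to code position. AF diagnosis position, principal diagnosis, admission source and index length of stay are not listed.

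**Analysis (section 8.7).** "A propensity score matching (PSM) 1:1 technique will be used to control for confounders when comparing each of the OAC cohorts vs. the apixaban cohort". In the matched outcome model, "Only the index drug will be the covariate, since other patient characteristics are expected to be similar already after the PSM". If matching leaves too few patients, a multivariable logistic regression is used: "The independent covariates in the regression analyses will include key patient demographics and hospital characteristics", with the final list still to be settled. No analysis by primary versus secondary AF is described, and section 8.9 does not mention the point as a limitation.

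**The concern.** A secondary AF code shows that AF was present during the stay, not that it caused the stay. An admission for pneumonia or heart failure with AF in the background may carry a different 1-month readmission risk from an admission for AF itself. It may also go with a different choice of anticoagulant. If the mix of the two types differs between cohorts after matching, part of the mix difference appears as a difference between drugs in the primary MB comparison and the secondary all-cause comparison.

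The protocol has the means to look at this. Section 8.4 says primary and secondary diagnoses are held for each hospitalization, and Table 2 requires first position for the MB and stroke readmission outcomes. Position is therefore used at readmission but not at index. Section 6 also cites a study in which longer initial stay, higher Charlson score and emergency-room admission predicted readmission. Of these, only Charlson is in Table 1.

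**Working it through.** **1. The plan's own figure.** Inputs from section 8.5: MB rate 1.4%, difference 0.5 points, two-sided alpha 0.05, 1:1 ratio, at least 30,000 patients per cohort. With 1.4% vs 0.9% and 80% power:

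n per arm = [1.960 × sqrt(2 × 0.0115 × 0.9885) + 0.842 × sqrt(0.014 × 0.986 + 0.009 × 0.991)]² / 0.005² = 7,137, or 14,274 in two arms.

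This is the 80% row of Table 3. All six rows reproduce as two-arm totals, although the column heading mentions one arm; that is a separate matter. At 30,000 per arm, power for 0.5 points exceeds 99%, so fairly small differences, real or spurious, can be detected.

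**2. What is already controlled.** Index heart failure, pulmonary disease, stroke/TIA and Charlson score are in Table 1. Section 8.2.2 excludes acute myocardial infarction, VTE, valve replacement, hip or knee replacement, pericarditis, myocarditis and dialysis or end-stage kidney disease. Both reduce differences in the reason for admission. Neither tells which diagnosis led to the stay. The imbalances below must therefore be read as what remains after matching.

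**3. Size on the difference scale, with no drug effect.** The documents give no AF-primary share and no risk by AF position, so these inputs are assumptions:
- residual imbalance in AF-primary share: 5 to 20 points
- risk difference between the two types of stay: 0.5 points for MB, 4 to 8 points for all-cause

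Spurious difference = imbalance × risk difference.

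Standard errors at 30,000 per arm:
- MB at 1.4%: sqrt(2 × 0.014 × 0.986 / 30,000) = 0.096 points
- All-cause at 18% (a rate cited in section 6): sqrt(2 × 0.18 × 0.82 / 30,000) = 0.314 points

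| Outcome | Imbalance (points) | Risk difference (points) | Spurious difference (points) | In SEs | Odds ratio |
|---|---|---|---|---|---|
| MB | 5 | 0.5 | 0.025 | 0.3 | 1.02 |
| MB | 15 | 0.5 | 0.075 | 0.8 | 1.05 |
| MB | 20 | 0.5 | 0.10 | 1.0 | 1.07 |
| All-cause | 5 | 4 | 0.2 | 0.6 | 1.01 |
| All-cause | 15 | 8 | 1.2 | 3.8 | 1.08 |
| All-cause | 20 | 8 | 1.6 | 5.1 | 1.11 |

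The MB figure of 0.075 points is 0.075 / 0.5 = 15% of the planned difference. The 30,000 is a count before matching; fewer matched pairs would lower the SE multiples.

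**4. Sensitivity on the ratio scale.** Let s be the share of AF-secondary stays (a apixaban, c comparator) and k the risk ratio of secondary to primary stays. With no drug effect, p_a = p_c × [1 + s_a(k − 1)] / [1 + s_c(k − 1)]. Comparator MB rate 1.4%, assumed k and shares, 30,000 per arm:
- k = 1.5, 60% vs 65%: p_a = 1.4 × 1.300/1.325 = 1.374%; difference 0.026 points; OR 1.02; rejection probability 6%.
- k = 2, 60% vs 80%: p_a = 1.4 × 1.6/1.8 = 1.244%; difference 0.156 points; OR 1.13; rejection about 38%.
- k = 3, 50% vs 80%: p_a = 1.4 × 2.0/2.6 = 1.077%; difference 0.323 points; OR 1.30; rejection 95%.

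For all-cause at 18%, k = 1.25 with 60% vs 65% gives 0.19 points (OR 1.01, rejection about 10%). With k = 2 and 60% vs 80% it gives 2.0 points (OR 1.15, rejection near 100%). The result depends almost entirely on the assumed inputs.

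**The case against.** **On wording.** Wherever the protocol describes patients as hospitalized for NVAF, the same sentence defines this as a primary or secondary code, so selection can be carried out without doubt. The objectives already speak of hospitalized NVAF patients. This stands. A reader might infer that the study cannot answer its question, or that admitting secondary codes is an error. The documents support neither: the pooled cohort is a stated design choice, and only the abstract's phrasing of the question sits badly with it.

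**On the covariates.** Section 8.7 does not list the propensity-score variables and defers detail to an SAP that is not shown, which could add the reason for admission. This stands in part: nothing confines the score to Table 1. But Table 1 is the protocol's own list of potential confounders, and it omits an index variable that the database holds. That is a gap in what the protocol fixes, not merely detail left for later.

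**On control.** A reader might infer that the reason for admission is uncontrolled. It is not: the comorbidity flags, Charlson score and exclusions act as proxies.

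**On size.** A reader might take the all-cause figure of 3.8 standard errors as the expected bias. It needs a 15-point imbalance that survives matching and the top of the assumed risk range, and it concerns a secondary outcome. The low end is 0.6 SE, and the primary-outcome figure is about 0.8 SE. An MB odds ratio of 1.30 needs a threefold risk ratio and a 30-point imbalance. New versus continuing anticoagulant use is a separate issue that code position would address only in part.

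**Conclusion.** The concern holds in a limited form. The protocol pools two types of index stay, lists no variable that separates them, and plans no look at the results by type, although diagnosis order is available. Control of the reason for admission is incomplete, not absent, and residual imbalance could bias both the MB and the all-cause comparison.

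Neither size nor direction can be derived from the documents. Under the assumed difference-scale inputs, the primary MB bias is small: 0.075 points at a 15-point imbalance. The all-cause bias ranges from 0.2 to 1.6 points, which at the upper end is well beyond sampling error. The stronger inference, that admission mix would account for an observed drug difference, is not supported, because no figure in the protocol gives the residual imbalance or the risk by AF position. The change should be made because it is cheap and lets the question be checked, not because a material bias has been shown.

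**What to change.** - **Table 1:** add AF diagnosis position at index (primary/secondary) and principal index diagnosis category.
- **Section 8.7:** include both in the propensity score and in the fallback regression, and check balance on them after matching.
- **Sensitivity analysis:** report 1-month MB and all-cause readmission separately for AF-primary and AF-secondary stays.
- **Wording:** use hospitalized patients with NVAF consistently, including in the abstract's research question.

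The cost is protocol and SAP text, two variables derived from diagnosis data already held, and one stratified table. Section 8.4 does not say whether admission source is held, so the fix does not depend on it.

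Exact matching on AF position is optional and has a price. With equal arms and a 15-point imbalance before matching, for example AF-primary shares of 40% and 25%, the largest share that can be paired is 25% + 60% = 85%. Up to about 15% of pairs, or 0.15 × 30,000 = 4,500, would be lost on this account alone. The remaining 25,500 per arm still exceed the 23,630 in Table 3's 95% row, even if that row is read as per arm, though other matching losses would come on top.

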**Variables:** Demographic, patient clinical characteristics, hospital characteristics, and key anticoagulant treatment-related information will be measured during the index hospitalization of NVAF patients. Other clinical characteristics (e.g. prior bleeding) of NVAF patients will be measured during a 12-month baseline period. The proportions of patients treated with apixaban, dabigatran, rivaroxaban, and warfarin that have MB-related, all-cause, and stroke-related readmissions that occur within 1 month of discharge of their initial hospitalization for NVAF will be evaluated. Hospital LOS and associated costs of MB-related and all-cause readmissions will be determined and compared between the other OAC cohorts and the apixaban cohort. Hospital cost data from the Premier database will reflect the hospital perspective (cost occurred to hospitals). Hospital LOS and associated costs of stroke-related readmissions will be evaluated by descriptive statistics as an exploratory analysis. Readmission rates, hospital LOS and costs associated with all-cause, MB-related and stroke-related readmissions occurring within 3 months of initial hospitalizations of hospitalized NVAF of patients will be evaluated by descriptive statistics as an exploratory analysis.

**Data sources:** The study will be conducted using the Premier Hospital database which is a nationally representative inpatient hospitalization records database that captures more than 45 million hospital discharges from greater than 600 acute care hospitals, representing approximately 20% of all hospital admissions in the U.S.

**Study size:** The preliminary data evaluation of the Premier database indicated that there are at least 30,000 patients for each of OAC cohort during the study period described for this study. With a two-sided test, an alpha-level of 0.05, and a 1:1 ratio of the comparison cohorts, and the assumed one-month MB-related readmission rate of 1.4%, and the assumed MB-related readmission rate difference of 0.5% between cohorts treated with other OACs vs. apixaban, we have estimated the following power calculation.

Power Calculation		
Nominal Power	Actual Power	N Total-One Arm
0.7	0.7	11,226
0.75	0.75	12,622
0.8	0.8	14,274
0.85	0.85	16,328
0.9	0.9	19,108
0.95	0.95	23,630

Thus, the study is expected to have sufficient sample sizes for the study measurements.

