## 8.2. Setting

Adult patients (age  $\geq 18$  years) hospitalized for NVAf, based on a primary or secondary discharge diagnosis code indicating NVAf, will be identified from the Premier Hospital database between January 1, 2013 and June 30, 2017. Patients who received apixaban, dabigatran, rivaroxaban, or warfarin during any time of the hospitalization (from admission to discharge) will be identified and grouped into study cohorts based on the OAC initiated. The first of such NVAf hospitalizations will be defined as the index hospitalization, with the corresponding hospital discharge date as the index date.

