### 8.2.3. Cohorts

After applying the inclusion and exclusion criteria, eligible patients will be assigned to the following cohorts based on the OAC treatment received during index hospitalizations.

1. **Apixaban Cohort:** NVAf patients who initiated apixaban during hospitalization
2. **Dabigatran Cohort:** NVAf patients who initiated dabigatran during hospitalization
3. **Rivaroxaban Cohort:** NVAf patients who initiated rivaroxaban during hospitalization
4. **Warfarin Cohort:** NVAf patients who initiated warfarin during hospitalization

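### The index stay is the first study-OAC hospitalization from January 2013 with no look-back into the 2012 data already held, so 2013 index stays can be recent repeat stays and later ones cannot

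*Protocol*

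**What the plan says.** Protocol section 8.1 sets the data period: "The overall study period will be from January 1, 2012 through September 30, 2017". Hospitalizations that can become the index "will be identified from the Premier Hospital database between January 1, 2013 and June 30, 2017". The index rule follows, in 8.1 and again in 8.2: "The first of such NVAF hospitalizations will be defined as the index hospitalization". The stays it refers to are NVAF stays in that window during which a study OAC was given.

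Section 8.1 gives the extra year, 2012, the role of a one-year baseline: "Other clinical characteristics (e.g. prior bleeding) of NVAF patients will be measured during a 12-month baseline period". Section 8.2.2 also uses a 12-month look-back for several excluded conditions and for edoxaban. It excludes no one for an earlier NVAF stay, or for earlier apixaban, dabigatran, rivaroxaban or warfarin. Table 1 lists neither an earlier NVAF stay nor the index year among the potential confounders.

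The index stay is nevertheless described as the first of its kind. Section 8.1 counts readmissions "within 1 month of discharge of their initial hospitalization for NVAF will be evaluated", and section 8.2.3 defines the apixaban cohort as NVAF "patients who initiated apixaban during hospitalization", with the same verb for the other three drugs.

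**The concern.** Take a patient given warfarin during an NVAF stay in December 2012 and readmitted with NVAF on warfarin in January 2013. Under the rule, the January stay is the index, is called initial, and counts as warfarin initiated. The study's own data show otherwise: in a study of readmissions, a readmission has become an index admission.

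The rule also changes meaning over the window. A 2013 index stay can follow a qualifying stay within the preceding 12 months. From 2014 it cannot, because the earlier stay would have been found first. If recently re-hospitalized patients have a higher readmission risk, and if the cohorts differ in how much of their use dates from 2012, they differ in their share of such patients. The listed matching variables do not address this directly. At stake is a small artificial difference in readmission rates, avoidable with data already in the study period.

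**Working it through.** **1. What the dates imply.** The window from January 2013 to June 2017 has 54 months. Only index stays in the first 12 of these (12/54 = 22% of calendar time) can have an uncounted qualifying stay in the preceding 12 months.

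**2. Share of recent repeats.** The documents give no repeat-stay counts, so this is an illustration.

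- From section 6: all-cause readmission of 18% by 1 month and 38% by 12 months (two different studies).
- Assumed: 30%, 50% or 80% of next stays qualify (AF code, one study OAC, same hospital); the hazard halves after month 12; first stays arise from 2010 at a constant or a declining rate.
- Monthly hazards before scaling by the qualifying share: month 1, −ln(0.82) = 0.198; months 2–12, (−ln(0.62) − 0.198)/11 = 0.0254; later, 0.0127.

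Simulating recurrent stays and applying the protocol's index rule gives these shares of patients with a qualifying stay in the 12 months before index:

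| | Share |
|---|---|
| Whole window, stable use (30 / 50 / 80% qualify) | 1.0 / 1.7 / 2.8% |
| Whole window, declining use | about 2–4% |
| 2013 index stays only, both patterns | about 5–13% |

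Rough check: 5–13% × 12/54 = 1.1–2.9%. Declining use puts more than 22% of patients into 2013, hence the upper end of 4%.

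**3. False odds ratio against a cohort with no recent repeats.** With base rate r0, repeat share s and relative risk RR (assumed 1.3–1.5), the observed rate is r = r0 × (1 + s × (RR − 1)). The false odds ratio is [r/(1 − r)] / [r0/(1 − r0)].

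- All-cause, r0 = 18%, s = 1%, RR = 1.3: r = 0.18054, odds ratio 1.004.
- All-cause, r0 = 18%, s = 4%, RR = 1.5: r = 0.1836, odds ratio 1.025. A steeper assumed decline gives 1.027.
- Major bleeding, r0 = 0.9%, s = 4%, RR = 1.5: r = 0.00918, odds ratio 1.02.

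**4. Precision for comparison (30,000 per arm, before matching loss).**

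- All-cause 95% half-width: exp(1.96 × √(2/(30,000 × 0.18 × 0.82))) − 1 = 4.3%.
- Major bleeding, with 30,000 × 1.4% = 420 and 30,000 × 0.9% = 270 events: exp(1.96 × √(1/420 + 1/270)) − 1 = 16.5%.

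**5. Direction.** It depends wholly on how repeats split by cohort. For major bleeding with RR 1.25–2.0, shares of 10% (comparator) against 2% (apixaban) give odds ratios of 1.02–1.08. Equal shares give 1.00, and 2% against 10% gives 0.98–0.93.

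**6. Room for exclusions.** The protocol's power table reproduces with pooled variance, two-sided alpha 0.05 and 1.4% against 0.9%. At 80% power, n = [1.960 × √(2 × 0.0115 × 0.9885) + 0.8416 × √(0.013804 + 0.008919)]² / 0.005² = 7,137 per arm, and 2 × 7,137 = 14,274, the tabulated value (a two-arm total). Losing 4% of 30,000 leaves 28,800. Even at 28,500, power is 99.99% for 1.4% against 0.9%, and 99.7% for 1.4% against 1.9%. At 18,000 (a 40% loss) it is still 99.4% and 96.1%.

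**The case against.** The January 2013 start is deliberate: it leaves a full baseline year, and 'initial' can be read as shorthand for a clearly defined index stay. Prior bleed, prior stroke/TIA, CHADS2, CHADS2-VASc and HAS-BLED draw on the baseline records and would adjust in part. The SAP may add matching variables. Recent repeats also enter by other routes in every year: an NVAF stay without a study OAC, a stay without AF, or a stay at another hospital. All of this stands and limits the size of the problem. It does not explain why the baseline year is used for other 12-month exclusions but not for an earlier qualifying stay.

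A reader might infer more: that repeats gather mainly in the older-drug cohorts and so tilt the result towards apixaban by construction. The documents do not support this. They give no uptake by drug. Section 6 says only that all three DOACs were available in the window, and that an earlier evaluation starting in January 2012 included apixaban. A patient with a 2012 stay on another drug could also be indexed on apixaban.

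A reader might also reach all-cause odds ratios of 1.06–1.09 by counting everyone with any 2012 stay. With RR 1.5, a 10% share gives r = 0.189 and an odds ratio of 1.06; a 15% share gives r = 0.1935 and 1.09. Those shares include patients indexed years after the 2012 stay, who are not recent repeats.

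**Conclusion.** The definitional gap is certain from the text: the first-stay search ignores a year of data that the study holds, and what counts as first differs between 2013 and later index dates. The numerical effect is small. Under the stated assumptions, about 1–4% of index patients over the whole window are recent repeats, and the false all-cause odds ratio is about 1.00–1.03 against a cohort with none. That lies inside the 4.3% half-width. For major bleeding the effect, at most about 1.02, is negligible against a half-width of about 17%. The direction is unknown.

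The size rests on splicing two studies' readmission rates, on the 30–80% qualifying share, on the halved later hazard and on the 1.3–1.5 relative risk. The last three have no source in the protocol. The change is worth making because it is cheap and removes a known calendar-dependent selection, not because the primary result is threatened.

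**What to change.** In the abstract and in sections 8.1 and 8.2, add a fixed 12-month rule: exclude patients whose index stay is preceded within 12 months by another captured NVAF hospitalization with a study OAC, using the 2012 baseline data already extracted. Report the number removed per cohort, which would also show how the repeats split by drug.

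A fixed rule is better than searching for the first stay over the whole period from January 2012. That search would give a look-back growing from 12 months for a January 2013 index to about 65 months for June 2017, and would drop patients for stays years earlier.

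The cost is one selection condition and one sentence, with no new data. The loss falls only on patients indexed in 2013, roughly 5–13% of that year's index stays under the assumptions above, which at least 30,000 per cohort can absorb. The rule does not establish new use of the drug, since section 8.9 states that outpatient treatment history is not available, and it leaves in patients whose recent stay had no study OAC or was at another hospital.
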